## 6.4. Analysis Methods

Continuous efficacy and health outcome variables, except for Systemic Lupus International Collaborating Clinics (SLICC)/American College of Rheumatology (ACR) Damage Index will use a restricted maximum likelihood-based mixed model for repeated measures (MMRM) analysis. The response variable will be change from baseline across postbaseline visits. The model will include the following explanatory variables as fixed factors: treatment, baseline disease activity (total SLEDAI-2K  $<10$ ;  $\geq 10$ ), baseline corticosteroid dose ( $<10$  mg/day;  $\geq 10$  mg/day prednisone or equivalent), region (North America, Central/South America/Mexico, Europe, Asia and Rest of World), visit (as categorical variable), baseline value, treatment-by-visit interaction, and baseline value-by-visit interaction. Within-patient variance-covariance errors will be modeled using an unstructured covariance matrix. If this analysis fails to converge, the following structures will be tested in this pre-specified order: 1) heterogeneous Toeplitz (TOEPH), 2) heterogeneous autoregressive (ARH[1]), 3) heterogeneous compound symmetry (CSH), and 4) autoregressive (AR[1]). The Kenward-Roger method will be used to estimate the degrees of freedom. For each treatment group the least squares mean (LS mean), standard error, within-treatment p-value, and 95% CIs will be reported.

Systemic Lupus International Collaborating Clinics (SLICC)/ACR Damage Index change from baseline will be summarized with observed and modified last observation carried forward (mLOCF).

The binary efficacy measures will be summarized with observed case and non-responder imputation (NRI).

For both efficacy and safety evaluations, if study drug is temporarily interrupted (suspended) during a treatment period, the measurements taken during the temporary interruption will be included in the analysis.

Both observed and imputed analyses will be performed for efficacy and health outcomes measures.

All analyses will include the treatment arms given in [Table JAIM.6.1](#).

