## 5. Study Design

### 5.1. Summary of Study Design

Study I4V-MC-JAIM (JAIM) is a Phase 3, multicenter, randomized, outpatient, long term extension trial to evaluate the long-term safety and efficacy of baricitinib 4-mg and 2-mg in eligible patients with systemic lupus erythematosus (SLE) who have completed the treatment period in an originating study (such as, Study I4V-MC-JAHZ [JAHZ] or Study I4V-MC-JAIA [JAIA]). Study JAIM will enroll patients who have completed treatment through week 52 of Study JAHZ or Study JAIA and meet eligibility requirements.

Abbreviations: QD = once daily; V = visit.

a Visit 1 of Study JAIM should be completed on the same calendar day as the Week-52 visit of the originating study.

b The follow-up visit should occur 4 weeks ( $\pm 5$  days) after the last dose of study drug.

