## 6. A Priori Statistical Methods

### 6.1. General Considerations

This Statistical Analysis Plan (SAP) describes analyses that will be utilized for the full clinical study report (CSR) for Study JAIM, at the time of JAIM primary outcome database lock. Analyses to be produced prior to the JAIM primary outcome database lock, for purposes of regulatory submissions, will be identified in the retained list of analyses. Additional safety analyses that integrate data from the originating studies will be specified in the integrated safety analysis plan (ISAP) for SLE. Any exploratory analyses will be described in a separate document. Statistical analysis of this study will be the responsibility of Eli Lilly and Company or its designee.

Not all displays described in this SAP will necessarily be included in the CSR. Not all displays will necessarily be created as a “static” display. Some may be incorporated into interactive display tools such as Spotfire instead of, or in addition to, a static display. Any display described in this SAP and not included in the CSR would be available upon request.

Throughout this document, references to analyses of corticosteroids refer to analyses of systemic corticosteroids, unless otherwise specified.

Statistical analyses of categorical safety and efficacy endpoints will be descriptive in nature.

Frequency counts and percentages by treatment arm (see [Table JAIM.6.1](#)) will be provided for the safety and efficacy endpoints. For non-model-based efficacy endpoints, 95% confidence intervals (CIs) for single proportions using the Wilson Score (Wilson, 1927; Newcombe, 1998) method will be utilized.

Unless otherwise stated, inferential statistical analyses (p-values and 95% CIs) which compare treatment groups will not be conducted.

For continuous efficacy and health outcomes endpoints the significance of within-treatment group changes from baseline will be evaluated by testing whether the treatment group least squares mean (LS mean) changes from baseline are different from zero; the 95% CI and the standard error for the LS mean change will also be displayed.

Change from baseline (defined in [Section 6.3](#)) will be calculated as the postbaseline (at that visit) value minus the baseline value. If all baseline values are missing for a particular variable, the change from baseline and percent change from baseline will not be calculated.

[Table JAIM.6.1](#) summarizes the treatment arms based on the treatment assigned in JAIM.

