### 6.3. Definition of Baseline and Postbaseline Periods

For efficacy analyses, *baseline* for patients receiving active treatment (baricitinib 2-mg and 4-mg) in originating studies (JAHZ and JAIA) is defined as the last nonmissing measurement taken in the originating studies, prior to starting study medication. *Baseline* for patients receiving placebo in originating studies is defined as the last nonmissing assessment prior to the first dose of active study drug given in Study JAIM Visit 1 (Week 0). Any assessment collected after the JAIM Visit 1 dose through the date of Visit 11 or the early discontinuation visit is defined as *postbaseline* for the Treatment Period.

Protocol-defined visit windows are defined as  $\pm 4$  days for Visit 2 (Week 4),  $\pm 7$  days for Visit 3 (Week 12),  $\pm 10$  days from Visit 4 (Week 24) until Visit 7 (Week 60), and  $\pm 14$  days from Visit 8 (Week 84) until Visit 11 (Week 156). If there are data within the protocol-defined window, those data will be used in by-visit analyses. If a protocol-defined visit is missing, then the nearest unscheduled visit data that exist will be mapped to that visit and included in by-visit analyses.

For safety analyses, baseline is defined as the last nonmissing scheduled (planned) measurement prior to the first dose of baricitinib administration in Study JAIM for continuous measures by-

visit analyses and all nonmissing measurements prior to the first dose of the study drug administration (baricitinib) in Study JAIM for all other analyses.

Postbaseline measures for the safety analyses are defined as the nonmissing scheduled (planned) measurements after the first dose of baricitinib administration in Study JAIM for continuous measures by-visit analyses and all nonmissing measurements after the first dose of the study drug administration (baricitinib) in Study JAIM for all other analyses.

In general, when the baseline measurement is collected on the same day (where time is not collected) as the first dose date, this measurement will be used as the baseline value for efficacy and safety except adverse events (AEs).

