Abbreviations: BICLA = British Isles Lupus Assessment Group-based Composite Lupus Assessment; BILAG = British Isles Lupus Activity Group; CNS = Central Nervous System; EQ-5D-5L = European Quality of Life5 Dimensions–5 Level; FACIT = Functional Assessment of Chronic Illness Therapy; mLOCF = modified last observation carried forward; mITT = modified intent-to-treat; MMRM = mixed model for repeated measures; NRI = non-responder imputation; NRS = Numeric Rating Scale; PCS = Physical Component Summary; SRI-4 = Systemic Lupus Erythematosus (SLE) Responder Index; SLEDAI-2K = Systemic Lupus Erythematosus Disease Activity Index 2000; SF-36 = Short Form 36; WPAI-Lupus = Work Productivity and Activity Impairment Questionnaire: Lupus V2.0.

a Assessments collected at multiple visits will be analyzed at each visit, in addition to the key time point listed below.

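### One covariance matrix and one baseline slope for all four arms will probably misstate per-arm SEs and CIs at early visits, where change spans about 56 weeks in continuing arms and 4 weeks in switching arms

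*SAP*

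**What the plan says.** SAP 6.4 specifies one REML MMRM for the continuous efficacy and health outcome measures (the SLICC/ACR damage index excepted), with change from baseline as the response. On the covariance it says "Within-patient variance-covariance errors will be modeled using an unstructured covariance matrix". Four fallback structures follow in case of non-convergence, and none is grouped by arm. Baseline enters as a main effect and by visit, with no term letting its slope differ by arm. All arms enter together: "All analyses will include the treatment arms given in" Table JAIM.6.1, which lists baricitinib 2-mg and 4-mg (continuing) and placebo to 2-mg and placebo to 4-mg (switching).

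SAP 6.3 gives the two sets different baselines. For continuing arms, baseline "is defined as the last nonmissing measurement taken in the originating studies, prior to starting study medication". For switching arms it is the last assessment before the first active dose at JAIM Week 0. SAP 5.1 fixes the gap: "Study JAIM will enroll patients who have completed treatment through week 52 of Study JAHZ or Study JAIA", and JAIM Visit 1 "should be completed on the same calendar day as the Week-52 visit of the originating study".

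The model's output is per arm. SAP 6.1 tests each arm's LS mean change against zero and adds that "the 95% CI and the standard error for the LS mean change will also be displayed". Footnote a of Table JAIM.6.4 extends this beyond the key time point: "Assessments collected at multiple visits will be analyzed at each visit". SAP 6.1 plans no between-arm inference unless otherwise stated.

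**The concern.** A single matrix assumes that, at each visit, the residual variance of change given baseline is the same in every arm. Here the interval over which change is measured differs 14-fold between arms at the first postbaseline visit. The correlation between two measurements usually weakens as they move apart, and protocol 3.2 describes SLE as highly variable over time. A 56-week change is therefore likely to leave more unexplained variance than a 4-week change.

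If so, the pooled variance lies between the two true values: too small for continuing arms and too large for switching arms. The Kenward-Roger method works within the assumed covariance model and does not repair a wrong one. With no between-arm tests planned, per-arm precision is all the inference this model delivers. In the switching arms the early visits are the first on active drug, so that is where onset of effect would be read.

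**Working it through.** **The plan's own figures.** There is no SD, correlation, SE or CI width to reproduce for any continuous endpoint. The one design figure is enrollment of about 1100. With 80% completing and 90% rolling over, it implies 1100 / (0.80 x 0.90) = 1528 originating patients, a number the documents do not give.

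**Step 1: interval behind the change (SAP 5.1, 6.3).** Continuing arms: 52 + w weeks at JAIM Week w. Switching arms: w weeks.

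| JAIM week | Continuing | Switching | Ratio |
|---|---|---|---|
| 4 | 56 | 4 | 14.0 |
| 12 | 64 | 12 | 5.3 |
| 24 | 76 | 24 | 3.2 |
| 48 | 100 | 48 | 2.1 |
| 156 | 208 | 156 | 1.33 |

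**Step 2: assumptions, none from the documents.** Two thirds of patients in continuing arms (367/367/183/183, which presumes 1:1:1 allocation in the originating studies); equal SDs (set to 1) and equal baseline means; complete data, so that the MMRM at one visit is close to an ANCOVA.

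**Step 3: formula.** Let r_c and r_s be the baseline-to-visit correlations in continuing and switching arms.
- Common slope: b = (2 r_c + r_s)/3.
- Effective residual variance in set k: V_k = (1 - r_k^2) + (r_k - b)^2. The second term is the misfit from forcing one slope.
- Pooled variance: P = (2 V_c + V_s)/3.
- Reported SE / true SE = sqrt(P/V_k). Coverage = 2*Phi(1.96 x ratio) - 1.

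Example at 0.3 vs 0.8: b = 0.467; V_c = 0.91 + 0.028 = 0.938; V_s = 0.36 + 0.111 = 0.471; P = 0.782. Ratios: sqrt(0.782/0.938) = 0.91 and sqrt(0.782/0.471) = 1.29.

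**Step 4: results at Week 4.**

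| r_c vs r_s | SE ratio, continuing | Coverage | SE ratio, switching | Coverage |
|---|---|---|---|---|
| 0.6 vs 0.6 | 1.00 | 95% | 1.00 | 95% |
| 0.6 vs 0.7 | 0.97 | 94.2% | 1.08 | 96.6% |
| 0.5 vs 0.7 | 0.95 | 93.7% | 1.13 | 97.4% |
| 0.3 vs 0.7 | 0.94 | 93.3% | 1.18 | 98.0% |
| 0.3 vs 0.8 | 0.91 | 92.7% | 1.29 | 98.8% |
| 0.2 vs 0.9 | 0.89 | 92.1% | 1.41 | 99.4% |

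Repeated ANCOVA simulations with 2000 to 6000 runs per scenario agree. Allowing for simulation noise, the ratios run about 0.87-0.97 in continuing arms (coverage about 91-94%) and about 1.05-1.45 in switching arms (about 96-99%). Omitting the slope-misfit term gives larger switching-arm ratios (1.42 at 0.3 vs 0.8).

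**Step 5: direction.** The result depends on follow-up variance as well as correlation. At 0.3 vs 0.7, residual variances become equal when follow-up variance in continuing arms is 0.51/0.91 = 56% of that in switching arms. At about that point the distortion is essentially gone; below it the direction reverses.

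**Step 6: later visits.** With correlations of 0.25 vs 0.45 assumed at Week 48, b = 0.317, V_c = 0.942, V_s = 0.815 and P = 0.900. The ratios are 0.98 and 1.05. By Week 156 the intervals differ only 1.33-fold.

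**Step 7: absolute size.** At 0.3 vs 0.8, the 95% half-width in a continuing arm is reported as 1.96 x sqrt(0.782/367) = 0.090 SD against a true 1.96 x sqrt(0.938/367) = 0.099 SD. In a switching arm it is 1.96 x sqrt(0.782/183) = 0.128 SD against 1.96 x sqrt(0.471/183) = 0.099 SD.

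**The case against.** The strongest reply is that elapsed time fixes neither variance nor correlation. A reader might infer from the 56- and 4-week spans that the intervals are wrong by construction. The documents do not support that. They give no SD or correlation for any endpoint; one set of arms has had a year of active drug while the other has just left placebo, so equal SDs are not assured; and the endpoints, from prednisone dose to joint counts to SF-36, need not persist alike. This stands, and the point is therefore stated as likely, not certain.

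A reader might also infer that the MMRM estimates are the only results planned for these endpoints. They are not: SAP 6.4 and 6.4.2.1 also plan observed-data summaries at each visit, which do not use the pooled matrix.

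The practical consequence is small. Efficacy is not primary (SAP 6.11.2), Table JAIM.6.4 makes Week 156 the key time point for these measures, the larger error is in the conservative direction, and half-widths move by about 0.01 SD in continuing arms and 0.03 SD in switching arms in a fairly strong scenario. A common covariance is also a conventional MMRM assumption. All of this bears on priority. It does not remove the point, because the unequal intervals come from the SAP's own baseline rule and the early-visit SEs, p-values and CIs are to be reported.

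**Conclusion.** The point holds in conditional form. The plan puts changes over very different intervals into one model with one covariance matrix and one baseline slope per visit. At early visits this probably understates the SE in continuing arms, by roughly 3-13%, and overstates it in switching arms, by roughly 5-45%. Those figures rest on the equal SDs, 2:1 split and range of correlations given above. Equal residual variances would remove the effect, and a smaller one in continuing arms would reverse it.

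It is mainly a matter for the first visits, is about 5% in switching arms by Week 48 under the correlations assumed there, and is negligible at Week 156. The primary safety objective is untouched. This is a cheap improvement, not a flaw that threatens the study's conclusions.

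**What to change.** In SAP 6.4, fit the MMRM separately for continuing and switching arms. Equivalently for this purpose, keep one model, group the unstructured covariance by continuing/switching, and let the baseline-by-visit slope differ by that group. Apply the existing fallback structures within group if a fit does not converge. Nothing planned is lost, since between-arm tests are not planned.

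Both parts matter. In simulation, grouping the variance alone restored about 95% coverage in the milder scenarios but gave 94-97% at 0.3 vs 0.8. Freeing the slope as well, or fitting separately, gave about 95% in every scenario.

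The cost is a few lines of SAP text and code, up to 10 x 11/2 = 55 more covariance parameters for 10 postbaseline visits, and group-specific slopes. Separate fits also make the region, baseline disease activity and corticosteroid effects group-specific. Non-convergence becomes somewhat more likely in small subsets, such as the WPAI scores restricted to patients employed at baseline, and with attrition over three years.

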### **6.4.1. Adjustments for Covariates**

Randomization in the originating studies is stratified according to disease activity (total SLEDAI-2K at screening  $<10$ ;  $\geq 10$ ), corticosteroid dose at baseline ( $<10$  mg/day;  $\geq 10$  mg/day prednisone or equivalent), and region (North America, Central/South America/Mexico, Europe, Asia and Rest of World). Therefore, these factors will be adjusted for as described in Section 6.4.

### **6.4.2. Handling of Dropouts or Missing Data**

Due to the long duration of JAIME, missing data that are imputed will be carried forward for the visit interval at Week 48, Week 108, and Week 156. Discontinued patients will not be included for evaluation in intervals subsequent to their discontinuation from the study. The following visit intervals are defined for NRI method and mLOCF method:

- Visit 6 (Week 48) [ $>$  Visit 1 (Week 0) and  $\leq$  Visit 6 (Week 48)]
- Visit 9 (Week 108) [ $>$  Visit 6 (Week 48) and  $\leq$  Visit 9 (Week 108)]
- Visit 11 (Week 156) [ $>$  Visit 9 (Week 108)]

#### **6.4.2.1. As-Observed Analysis**

The “as-observed” strategy is used in so-called “observed cases” or “completers” analysis, ubiquitous in the literature, but is not one of the recommended strategies in the ICH E9(R1). For this analysis, only data from completers at the visit are relevant, and therefore the analysis does not need to deal with missing data. This estimand is based on the subset of patients who would complete treatment through Visit X if assigned to it. Therefore, this estimand is conditional and targets the effect of treatment conditional on completion of treatment through the time point of interest. Because the estimand is defined for a subpopulation conditional on an intercurrent event, it is not causal. Summaries based on observed data at each postbaseline visit will be provided.

#### **6.4.2.2. Non-responder Imputation (NRI)**

The NRI method may be used when the estimand of interest uses the composite strategy (EMA 2020) for handling intercurrent events. In this strategy, patients with any intercurrent event that leads to the permanent discontinuation of assigned study treatment or to prohibited medication use are defined to have failed treatment for that particular visit interval but not for the subsequent visit intervals (as defined in Section 6.4.2). Therefore, using a composite estimand approach, no data would be missing and the function of the NRI is to estimate the estimand.

All patients who discontinue the study or permanently discontinue study treatment at any time for any reason or patients who have a prohibited medication in a particular visit interval will be defined as non-responders for that visit interval and excluded from the subsequent visit intervals. Enrolled patients without at least one postbaseline observation will be defined as non-responders for the first visit interval (Visit 6) and excluded from evaluation in subsequent visit intervals.

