5.4. Justification for Dose

The 4-mg and 2-mg QD doses of baricitinib selected for this study are based on the Phase 2 SLE study, Study JAHH, and are additionally supported by pharmacokinetic (PK), safety, and efficacy data for baricitinib in Phase 2 and Phase 3 RA studies and the Phase 2 psoriasis study. If, after final analysis of the SLE Phase 3 originating studies, it is determined that either dose of baricitinib does not have a positive benefit/risk profile, then that dose arm may be discontinued and all patients transferred to the remaining dose arm.

In the Phase 2 SLE study, baricitinib 4-mg QD demonstrated statistically significant efficacy compared to placebo across several relevant measures, including remission of arthritis and/or rash (SLEDAI-2K), SRI-4, flare, and LLDAS. Baricitinib 2-mg QD was numerically better than placebo across these measures, although the results were not statistically significant. Dose response patterns favoring baricitinib 4-mg were evident across measures, and improvement was observed for both doses in patient-reported outcomes, including worst pain and worst joint pain. Pharmacokinetic/pharmacodynamic (PK/PD) modeling suggests the maximum response after dosing with 2-mg was not attained by 24 weeks. Therefore, there is potential that baricitinib 2-mg will also demonstrate efficacy at Week 52. No notable safety findings emerged compared to the results from baricitinib studies for other indications.

In Phases 2 and 3 RA studies, baricitinib 4-mg QD has demonstrated consistent efficacy; baricitinib 2-mg QD was also effective, but was less consistent than 4-mg QD across measures of efficacy and patient populations. Both doses were acceptably safe and well tolerated in the context of the efficacy observed and the benefit/risk profiles of other disease-modifying antirheumatic drugs. There was no substantial increase in efficacy noted with doses higher than 4-mg, where studied.

In the Phase 2 psoriasis study, baricitinib doses between 4-mg and 10-mg were associated with statistically significant reductions in measures of disease activity, with greater efficacy at the higher doses. The 2-mg dose did show numeric improvements in efficacy compared with placebo. The 8-mg and 10-mg doses were associated with a higher frequency of AEs related to laboratory abnormalities (decreases in hemoglobin, neutrophils, and lymphocytes), while the 2-mg and 4-mg dose groups had a pattern of AEs similar to placebo.

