7.4. Dosage Modification

During this study, treatment assignment and dose adjustment of investigational product will be followed strictly as indicated in Section 7.2.1 and Section 7.2.2.

If, after final analysis of the SLE Phase 3 originating studies, it is determined that either dose of baricitinib does not have a positive benefit/risk profile, then that dose arm may be discontinued and all patients transferred to the remaining dose arm. This modification would be made via an amendment to this protocol.

See Section 7.7 for permitted concomitant therapy.

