10.3.3.1. Missing Data Imputation

Missing data will be imputed at specified time points utilizing methodologies, including the following:

- Modified Last Observation Carried Forward: The last observed value (non-missing value) is used to fill in missing values at a later time point.
- Nonresponder imputation: Patients who discontinue treatment early will be defined as nonresponders.

The SAP will stipulate which methodology will be utilized for specific analyses.

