Appendix 3.3. Study and Site Closure

Appendix 3.3.1. Discontinuation of Study Sites

Study site participation may be discontinued if Lilly or its designee, the investigator, or the ERB of the study site judges it necessary for medical, safety, regulatory, or other reasons consistent with applicable laws, regulations, and GCP.

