Appendix 3.3.2. Discontinuation of the Study

The study will be discontinued if Lilly or its designee judges it necessary for medical, safety, regulatory, or other reasons consistent with applicable laws, regulations, and GCP.

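### SAP 6.4.2.2 would score patients stopped by a sponsor's site or study closure as treatment failures, lowering NRI response rates in intervals open at closure, above all at Week 156

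*SAP*

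**What the plan says.** SAP 6.4.2.2 describes the estimand behind non-responder imputation (NRI) as a composite one: "patients with any intercurrent event that leads to the permanent discontinuation of assigned study treatment", or to use of prohibited medication, have failed. The operative rule follows: "All patients who discontinue the study or permanently discontinue study treatment at any time for any reason", together with users of prohibited medication, "will be defined as non-responders for that visit interval and excluded from the subsequent visit intervals". The intervals, set in SAP 6.4.2, end at Weeks 48, 108 and 156. Protocol 10.3.3.1 has the same rule in shorter form: "Patients who discontinue treatment early will be defined as nonresponders".

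The protocol also names stops that the sponsor may initiate. Appendix 3.3.2 says: "The study will be discontinued if Lilly or its designee judges it necessary for medical, safety, regulatory, or other reasons". Appendix 3.3.1 says: "Study site participation may be discontinued if Lilly or its designee, the investigator, or the ERB of the study site judges it necessary". Protocol 8.2 treats ending participation on such grounds as discontinuation from the study, so these patients fall within the NRI wording. For a dose arm judged unfavourable, Protocol 5.4 and 7.4 foresee something different: "then that dose arm may be discontinued and all patients transferred to the remaining dose arm", and 7.4 adds "This modification would be made via an amendment to this protocol".

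Table JAIM.6.4 gives Week 156 as the key time point for every endpoint analysed with NRI, including SRI-4 to SRI-8, LLDAS, CLASI, BICLA and organ-system improvement. Each is also summarised on observed cases (SAP 6.4). Response rates carry Wilson intervals, and no between-group inference is planned (SAP 6.1).

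**The concern.** A composite strategy turns an intercurrent event into a failure because the event is taken to say something about how treatment went for that patient. A site or study closure need not say anything of the kind. Under the rule as written, a patient in response at the last visit before closure becomes a non-responder for that interval because of a calendar date.

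At stake are the absolute response rates and their Wilson intervals, which are the planned output for these endpoints. The interval would sit around a rate that mixes response with the share of patients cut off. The Week 156 interval is the last to close for every patient, so an early end to the study reaches it first. Unlike a dose-arm change, site or study closure is not tied by the protocol to an amendment, so nothing would automatically bring the NRI rule back for review.

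**Working it through.** **No plan figure to reproduce.** The documents give no response, dropout or closure figure for JAIM. The planned enrolment of about 1100 plays no part in the argument.

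**Inputs.**
- Rule: failure in the interval of the stop, removal from later ones, no exception by reason (SAP 6.4.2.2).
- Intervals: Weeks 0–48, 48–108 and 108–156 (SAP 6.4.2).
- Illustrative response rates p: 64.4% (4-mg) and 51.4% (2-mg), the Phase 2 Week 24 SRI-4 rates in Protocol 3.1, used here only as assumptions.
- Assumed: entry period, closure date, no other dropout, response unrelated to closure.

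**Step 1: general formula.** If a share c of the patients evaluated in an interval is stopped by closure, the NRI rate is p × (1 − c).

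| c | p = 64.4% | p = 51.4% |
|---|---|---|
| 5% | 61.2% | 48.8% |
| 10% | 58.0% | 46.3% |
| 20% | 51.5% | 41.1% |
| 30% | 45.1% | 36.0% |
| 50% | 32.2% | 25.7% |

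For example, 64.4% × (1 − 0.20) = 51.5%.

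**Step 2: what c could be if the whole study closed.** Let entry be uniform over E weeks and let the study close T weeks after first entry. A patient entering at week e is followed for the smaller of T − e and 156 weeks. For each interval, 1 − c is the share of patients who entered it and reached its end.

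Worked case, E = 104 and T = 182:
- Week 48: everyone reaches it, so the rate is 64.4%.
- Week 108: needs e ≤ 74, so 74/104 = 71.2%, and 0.644 × 0.712 = 45.8%.
- Week 156: needs e ≤ 26 among the 74, so 26/74 = 35.1%, and 0.644 × 0.351 = 22.6%.

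| E | T | Week 48 | Week 108 | Week 156 |
|---|---|---|---|---|
| 104 | 130 | 50.8% | 17.3% | 0.0% |
| 104 | 156 | 64.4% | 29.7% | 0.0% |
| 104 | 182 | 64.4% | 45.8% | 22.6% |
| 104 | 208 | 64.4% | 61.9% | 33.5% |
| 104 | 260 | 64.4% | 64.4% | 64.4% |
| 52 | 130 | 64.4% | 27.2% | 0.0% |
| 52 | 182 | 64.4% | 64.4% | 32.2% |
| 52 | 208 | 64.4% | 64.4% | 64.4% |

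True response is 64.4% in every cell. All variation comes from entry and closure dates. The zeros occur only where the study ends no later than 156 weeks after first entry, so that essentially nobody could reach Week 156. They are built into those scenarios.

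**Step 3: the same cases with closure taken out of the failure event.** If visits not yet due leave the denominator, the rate returns to 64.4% wherever visits did fall due. In the zero cells the Week 156 rate becomes not estimable; it does not become 64.4%.

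**The case against.** Much can be said on the other side.

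- **Only open intervals are affected.** Intervals completed before closure keep their rates, and stopped patients leave later denominators. A reader might infer that the responder rates as a whole end up measuring the closure date. That does not follow.
- **Observed-case summaries are planned for every binary measure.** They would not fall in this way, and a gap between the two would be visible. This stands, but SAP 6.4.2.1 itself places the observed-case approach outside the strategies of the E9(R1) addendum and calls it non-causal. NRI is the only binary analysis tied to such a strategy.
- **Dose-arm closure is a transfer.** A reader might infer that a closed dose arm would show a collapse in response. The protocol moves those patients to the other dose, by amendment. The operative NRI sentence speaks of stopping study treatment; only the estimand sentence says *assigned*. Their status is undefined, and that is all the text supports.
- **Closure may be informative.** Appendices 3.3.1 and 3.3.2 allow it for medical or safety reasons. Treating every closure as unrelated to outcome would be an assumption too, so both versions should be shown.
- **Efficacy is secondary and descriptive, and a closure may never happen.** This limits the importance of the point. It does not make the rule right for an event that the protocol names.

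**Conclusion.** The point holds in a limited form. SAP 6.4.2.2 states a rule without exception by reason, Protocol 10.3.3.1 agrees with it, and the protocol foresees site and study closure. If the sponsor closes sites or the study, NRI response rates in intervals then open are biased downward to p × (1 − c), with Week 156 the most exposed. At an assumed p of 64.4%, the rate is 61.2% if 5% of the interval's patients are affected, 51.5% if 20%, and 32.2% if 50%.

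These sizes rest on assumed response rates, on closure being unrelated to response, and on enrolment and closure timing that the documents do not give. With late enough closure the effect is nil. The near-zero Week 156 rates in the most extreme scenarios should not be read as a forecast. No between-arm test is touched, because none is planned. This is an inexpensive improvement to a secondary, descriptive analysis.

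**What to change.** In SAP 6.4.2.2:

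1. Exclude site or study closure by the sponsor from the NRI failure event. Keep data up to the stop, and take visits not yet due at closure out of the denominator. Apply the due-date rule also to patients who had already left for their own reasons; otherwise late entrants could add failures but never responses. Report a rate as not estimable where no due visits remain.
2. Report the number of patients censored this way, by arm and interval.
3. Show NRI also with these stops counted as failures, since a closure for medical or safety reasons may be related to outcome.
4. State whether a dose-arm transfer, if made by amendment, counts as discontinuing the assigned treatment for NRI.
5. Describe and justify the departure from Protocol 10.3.3.1 in the clinical study report, as Protocol 10.3.1 asks for changes that do not alter a principal feature.

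The cost is SAP wording, a filter on the reason for stopping, and one extra set of NRI tables. The downside is that closure reasons must be classified. SAP 6.7 names a category for COVID-19 logistics but shows none for closure, and Appendix 3.3.1 also lets the investigator or ethics board close a site, so the classification must say how those closures count.
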